#### **Descriptive Summary of Safety**

The incidence of hypoglycemia confirmed by SMBG (total and severe) and the percentage time (by CGM) with glucose below 70 mg/dL and below 54 mg/dL will be reported. Nocturnal is defined as midnight to 0600 and severe hypoglycemia is defined as an event requiring assistance of another person to actively administer carbohydrate, glucagon, or other resuscitative actions.

The number and percentage of subjects with treatment-emergent AEs will be tabulated by system organ class and preferred term by relationship to treatment and by severity.

A summary table by study visit with descriptive statistics for  $FEV_1$  at screening and end of study will be provided. The  $FEV_1$  data will also be presented graphically.

Confidential Page 11 of 70

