### 3.9.2.6 Hypoglycemic Events

A hypoglycemic episode is defined as any event with SMBG <70 mg/dL (i.e., Level 1 hypoglycemia) or SMBG <54 mg/dL (i.e., Level 2 hypoglycemia) (ADA 2021a) on the study-provided glucose meter. Severe hypoglycemic events are defined as events requiring assistance of another person to actively administer carbohydrate, glucagon, or other resuscitative actions. Severe hypoglycemic events will be documented as SAEs in the CRF. Nonsevere hypoglycemic events will not be documented as AEs but will be recorded in the hypoglycemia page of the CRF.

After the standardized meal challenge at Visit 2, subjects will be monitored for signs of hypoglycemia. Subjects exhibiting signs of hypoglycemia will be treated as appropriate (e.g., provided with a snack or glucose). The type of treatment given and time will be recorded and subjects will remain in-clinic until hypoglycemia is resolved.

In the event that the subject accidentally enters carb intake/meal announcement for a certain meal and also doses with Afrezza, carbohydrates or glucagon should be administered. The subject should be instructed to contact the Investigator and site staff as soon as possible following the event to ensure prompt review and to give the Investigator the opportunity to address any further necessary measures for correction.

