### 5.4.1 Safety Endpoints

- Event rates and incidence Level 1 (<70 mg/dL) and Level 2 (<54 mg/dL) hypoglycemic events as confirmed by SMBG
- Event rates and incidence of severe hypoglycemic events, defined as events requiring assistance of another person to actively administer carbohydrate, glucagon, or other resuscitative actions
- Incidence and severity of AEs: TEAEs, SAEs, AESIs, and device complaints
- Change in FEV1 from screening to end of study

Confidential Page 62 of 70

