8.1 Study Objectives

The primary objective of this study is to evaluate the change in HbA1c from baseline to end of study in adults ≥ 18 years of age with T1DM for each of the three following groups:

- AfreZZa + AID: AfreZZa for bolus (mealtime) in combination with use of a CSII pump with an AID algorithm using a RAA for basal and correction insulin coverage
- AfreZZa + Insulin Degludec: AfreZZa for bolus (mealtime and correction) in combination with insulin degludec for basal insulin coverage
- AID Control: CSII pump with an AID algorithm using an RAA for all bolus (mealtime and correction) and basal insulin coverage

The secondary objectives of this study are to:

Evaluate the safety of study treatment based on hypoglycemia event rate, based on SMBG (self-monitored blood glucose testing), and severe hypoglycemia incidence rate in adults ≥ 18 years of age with T1DM for each of the three following groups:

- AfreZZa + AID
- AfreZZa + Insulin Degludec
- AID Control

Evaluate the impact of study treatment on overall glycemic control when comparing baseline versus end of treatment period as measured by core CGM metrics based on G6 Pro data:

- Change in percent time in range (TIR), defined as time spent with glucose in the range of 70 to 180 mg/dL
- Change in percent time below range (TBR), defined as time spent with glucose < 70 mg/dL
- Change in percent time spent with glucose < 54 mg/dL

- Change in percent time above range (TAR), defined as time spent with glucose >180 mg/dL
- Change in percent time spent with glucose >250 mg/dL
- Change in glycemic variability as measured by coefficient of variation (CV)

The above metrics to be evaluated on each of the three following groups in adults ≥ 18 years of age with T1DM for each of the three following groups:

- Afrezza + AID
- Afrezza + Insulin Degludec
- AID Control

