8.2.4 Descriptive Summary of Safety

The incidence (number of events) of hypoglycemia confirmed by SMBG (total and severe) and the percentage time (by CGM) with glucose below 70 mg/dL and below 54 mg/dL will be reported. Nocturnal is defined as midnight to 0600 and severe hypoglycemia is defined as an event requiring assistance of another person to actively administer carbohydrate, glucagon, or other resuscitative actions. The number and percentage of subjects with treatment-emergent AEs will be tabulated by system, organ class, and preferred term by relationship to treatment, and by severity.

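### Read literally, SAP 8.2.4 and the synopsis count a severe hypoglycemic event only if a meter reading confirms it, contrary to the severe definition, the endpoints, SAP 8.1 and protocol 5.15

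*SAP*

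**What the plan says.** The reporting sentence in SAP 8.2.4 gives the incidence, as a number of events, of "hypoglycemia confirmed by SMBG (total and severe", followed by the closing bracket and the CGM time-below-range measures. The synopsis, under Descriptive Summary of Safety, has the same construction: "The incidence of hypoglycemia confirmed by SMBG (total and severe".

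The next sentence in each place defines the severe category without reference to a meter. In the SAP, "severe hypoglycemia is defined as an event requiring assistance of another person to actively administer carbohydrate, glucagon, or other resuscitative actions". Protocol 3.9.2.6 agrees: "Severe hypoglycemic events are defined as events requiring assistance of another person to actively administer carbohydrate, glucagon, or other resuscitative actions".

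The endpoints keep the two kinds of event apart. In the synopsis and in protocol 5.4.1, SMBG confirmation belongs to the Level 1 and Level 2 bullet. The severe bullet stands alone: "Event rates and incidence of severe hypoglycemic events, defined as events requiring assistance of another person". SAP 8.1 makes the same split, with the hypoglycemia event rate "based on SMBG (self-monitored blood glucose testing), and severe hypoglycemia incidence rate" listed as a second item. Protocol 5.15, the analysis section in the body of the protocol, lists total, nocturnal and severe hypoglycemia with no SMBG qualifier.

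Two other places bear on the total. Protocol 3.9.2.6 defines a hypoglycemic episode by a value below 70 mg/dL on the study meter, and Table 3 footnote f defines episodes as SMBG measurements below that level. Section 3.9.2.6 also sends severe events to the SAE record and nonsevere events to the hypoglycemia page of the CRF.

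**The concern.** The reporting rule adds a condition that the endpoint does not have. SMBG is measured by the subject. A subject who needs someone else to give carbohydrate or glucagon is plausibly less able to take a reading, although the documents do not say so. If that is right, the events most exposed to the added condition are the gravest ones.

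Severe hypoglycemia incidence is a named secondary objective (protocol 2.2, SAP 8.1). Protocol 1.3.1 lists severe hypoglycemia as an important identified risk of Afrezza, and discontinuations for it are one of two specific grounds in protocol 6.1.5 on which the sponsor may stop the study. The study draws no statistical inference (protocol 5.6), so the descriptive tables are the result. A hypoglycemia table that disagrees with the SAE listing in the same report would leave a reader unsure which count answers the objective.

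**Working it through.** The documents give no event rate or expected count, so there is no planned figure to reproduce. The check is a comparison of texts, followed by a calculation of scale.

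**Step 1. What each place requires of a severe event**

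| Place | Requirement |
|---|---|
| SAP 8.2.4, reporting sentence | SMBG confirmation |
| Synopsis, Descriptive Summary of Safety, reporting sentence | SMBG confirmation |
| SAP 8.2.4 and synopsis, the sentence that follows | Another person's assistance; no glucose value |
| Protocol 3.9.2.6 | Another person's assistance; no glucose value |
| Synopsis endpoints and protocol 5.4.1 | Separate bullet; SMBG attached to Level 1 and Level 2 only |
| SAP 8.1 | SMBG attached to the event rate; severe incidence listed separately |
| Protocol 5.15 | No SMBG qualifier |

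Two reporting sentences carry the condition. Every other place leaves it off.

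**Step 2. One event traced through the plan**

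Take a subject who is given glucagon by a relative, with no reading on the study meter.
- Under the SAP 8.2.4 sentence it is counted neither as severe nor in the total.
- Under protocol 5.15 it is counted as severe. Its place in the total is still unclear, because the episode definition in 3.9.2.6 and Table 3 footnote f needs a meter value.
- In the SAE record it is present (3.9.2.6). If treatment-emergent, it is also in the AE table.

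**Step 3. Scale of one omitted event**

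Arm sizes are given in SAP 7.1 and follow from 25 subjects at 2:2:1: 25 × 2/5 = 10, 25 × 2/5 = 10, 25 × 1/5 = 5. SAP 8.2.4 glosses incidence as a number of events, and on that basis the table shows 0 instead of 1. As a proportion of subjects, x/n with exact (Clopper-Pearson) 95% limits:

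| Arm | Event omitted | Event counted | Change |
|---|---|---|---|
| Either Afrezza arm, n = 10 | 0/10 = 0% (0 to 30.8%) | 1/10 = 10% (0.3 to 44.5%) | 10 points |
| AID Control, n = 5 | 0/5 = 0% (0 to 52.2%) | 1/5 = 20% (0.5 to 71.6%) | 20 points |

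The proportions assume that the subject has no other severe event.

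**Step 4. Chance that at least one event is omitted**

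Let q be the share of severe events without a reading and k the number of severe events. The documents give neither; the values below are assumptions, and events are treated as independent. The chance is 1 − (1 − q)^k.

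| q (assumed) | k = 1 | k = 2 | k = 3 |
|---|---|---|---|
| 10% | 10% | 19% | 27% |
| 25% | 25% | 44% | 58% |
| 50% | 50% | 75% | 88% |

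For example, with q = 25% and k = 3: 1 − 0.75³ = 0.578. If no severe event occurs, nothing is omitted.

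**The case against.** The strongest reply is that this is a loosely placed modifier and not an exclusion rule. Neither document states that severe events without a reading are to be excluded. The severe definition follows directly in the same paragraph, and the endpoints, SAP 8.1 and protocol 5.15 all point to the intended reading. An analyst who took the plan as a whole would probably count the event. This stands as a limit: the documents conflict, and most of them are on the right side. It does not remove the problem, because the SAP is the document that specifies the analysis, and its bracket expressly names severe events among those to be confirmed.

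A reader might infer that severe events would be lost from the study. The documents do not support that. They are recorded as SAEs (3.9.2.6, 4.2.1), notified within 24 hours (4.2.3), included in the AE endpoints (5.4.1) and covered by the individual data listings (5.3). The exposure is confined to the hypoglycemia table and its agreement with the safety tables.

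A reader might also infer that the severe count is understated by a definite percentage. No share of unmetered events appears in either document. Exclusion criterion 16 removes subjects with a severe event in the prior 180 days, and the number of severe events may be zero.

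Nor should the absence of a stated reconciliation step be held against the plan. The data management sections of the SAP are redacted and may contain one.

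**Conclusion.** The conflict is real and rests on the wording alone. Two reporting sentences put a meter condition on severe hypoglycemia that the definition, the endpoints, the SAP objective and protocol 5.15 do not have. Two analysts following different parts of the plan could report different severe counts from the same data.

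The practical effect is uncertain and bounded. It arises only if a severe event occurs without a confirming reading and the SAP sentence is applied literally. In arms this small, a single event then decides whether the table reads zero. The omission from the total has a second source, the meter-based episode definition, so correcting the two reporting sentences alone would leave that part unresolved. The matter should be settled before database lock, as a correction to the definition of a secondary safety summary. It does not show that severe events go unrecorded.

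**What to change.** - In SAP 8.2.4 and the synopsis, restrict SMBG confirmation to Level 1 and Level 2 events. Count severe events by the assistance definition, whatever the meter shows and whether or not a reading exists.
- State that the total is the SMBG-confirmed events plus any severe events without a confirming meter value, each event counted once.
- Align the episode definition used for analysis (protocol 3.9.2.6 and Table 3 footnote f) with that total, so that the table and the definition agree.
- Reconcile the severe count with the SAE records before database lock. If useful, report how many severe events had a meter value.

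The cost is a wording change in the SAP, the synopsis and the two definitions, plus one reconciliation check. No new data are needed, since severe events are already captured as SAEs, and clinical management is unchanged. The downside for the sponsor is that the reported severe count may be slightly less favourable.

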8.3 General Considerations

All statistical processing will be performed using the most current version of statistical software (such as MiniTab, MATLAB, or Microsoft Excel) at the time of the analysis.

Summary tables (descriptive statistics and/or frequency tables) will be provided for screening and/or baseline variables, efficacy variables, and safety variables.

Continuous variables will be described by descriptive statistics (n, mean, median, standard deviation, minimum, and maximum). Frequency counts and percentage of subjects within each category will be provided for categorical data. Individual data will be listed and sorted by treatment, subject ID, visit, and time point. Database lock will occur upon the completion of the study.

Signatures for

I am the Author of this document:

Name: **[name]**
[name]

As the Author I approve this document

2022-03-30 19:35:41 (UTC-07:00)

Electronically Signed in

Timestamp

Content Approval:

I approve this Content

Name: **[name]**
[name]

2022-03-30 19:40:40 (UTC-07:00)

Electronically Signed in

Timestamp

Content Approval:

I approve this Content

Name: **[name]**
[name]

2022-03-30 20:39:27 (UTC-07:00)

Electronically Signed in

Timestamp
